5.2 Plans for future product development and testing

This Phase II study is on the critical path to efficacy evaluation of this prime-boost approach. If found to be sufficiently safe, tolerable and immunogenic, the efficacy evaluation will compare prime-boost to placebo. This design could be altered if HVTN 204 does not demonstrate that the prime-boost is sufficiently safe or immunogenic.

STUDY DESIGN

6 Study objectives

6.1 **Primary objectives**

Safety

• Evaluate the safety and tolerability of 3 VRC HIV-1 DNA-6-plasmid vaccine doses at 4.0 mg/dose followed by VRC HIV-1 rAd5 vaccine boost at 10¹⁰ PU in HIV-1 uninfected adults.

Immunogenicity

• Evaluate the immunogenicity of 3 VRC HIV-1 DNA-6-plasmid vaccine doses at 4.0 mg/dose followed by VRC HIV-1 rAd5 vaccine boost at 10¹⁰ PU in HIV-1 uninfected adults.

6.2 Secondary objectives

Immunogenicity

- To evaluate the frequency of humoral immune responses to 3 doses of the HIV-1 DNA vaccine followed by the adenoviral vector vaccine. Humoral immunogenicity at 4 weeks post final vaccination will be assessed by neutralizing antibody and binding assays.
- To assess the relationship between prior Ad5 neutralizing antibody and immunogenicity as assessed by IFN- γ ELISpot, ICS, and neutralizing antibody assay.
- To evaluate the frequency and durability of cellular immunogenicity.
- To characterize the magnitude and breadth (defined as response to individual peptide pools) of the vaccine-induced HIV-specific T-cell responses as measured by the IFN- γ ELISpot and ICS assays.
- To evaluate the cross-clade cellular responses to HIV-1 Gag, Pol, and Nef peptides from clades A and C as assessed by the IFN- γ ELISpot and ICS.

Social impacts

To evaluate the social impacts of trial participation.

7 Study type, study population, and eligibility criteria

The study is a Phase II multicenter, randomized, placebo-controlled, double-blind trial to evaluate the safety and immunogenicity of VRC-HIVDNA016-00-VP followed by VRC-HIVADV014-00-VP. Participants will be healthy HIV-1-uninfected (seronegative) adults, 18-50 years of age, who comprehend the purpose of the study and have provided written informed consent. Participants will be recruited and screened; those determined to be eligible will be enrolled in the study and followed for a period of 12 months.

Participants will receive injections at 4 time points, administered at 0, 1, 2, and 6 months (see Overview). All injections will be administered by intramuscular injection in the outpatient setting.

See Table 7-1 for inclusion criteria and Table 7-2 for exclusion criteria. Final eligibility determination will depend on results of laboratory tests, medical history, physical examinations, and answers to the self-administered and/or interview questions.

See Section 12 for screening procedures.

HVTN204_v1_PLoS Review.doc

45

Table 7-1 Study inclusion criteria

Investigators should always use good clinical judgment in considering a volunteer's overall fitness for trial participation. Some volunteers might not be appropriate for enrollment even if they meet all inclusion /exclusion criteria because medical, psychiatric, or social conditions might make evaluation of safety and / or immunogenicity difficult.

General

Age: 18 to 50 years

Access to a participating HVTU and willingness to be followed for the planned duration of the study

Assessment of understanding: Complete a questionnaire prior to first vaccination; verbalize understanding of all questions answered incorrectly

Willingness to receive HIV test results

Informed consent: Be able and willing to provide informed consent

Health: Be in good general health as shown by medical history, physical exam, and screening laboratory tests performed within 56 days of enrollment.

Laboratory

Hemoglobin: \geq sex-specific institutional lower limit of normal and at least 11.0 g/dL for women, 12.5 g/dL for men

WBC count = 3,300 to 12,000 cells/mm³

Total lymphocyte count $\ge 800 \text{ cells/mm}^3$

Remaining differential either within institutional normal range or accompanied by site physician approval

Platelets = 125,000 to 550,000 cells/mm³

ALT does not exceed 1.25 the upper limit of institutional normal ranges

Creatinine does not exceed institutional upper limit of normal

Negative HIV blood test: US participants must have a negative FDA-approved ELISA test. Non-US sites will use locally available and locally approved assays

Normal urine:

- Negative urine glucose and
- Negative or trace urine protein

Additional inclusion criteria for female participants

Negative serum or urine β -HCG pregnancy test performed on the day of initial vaccination prior to vaccination Reproductive status: a female participant must:

- agree to consistently use contraception for at least 21 days prior to enrollment until 9 months post enrollment, for sexual activity that could lead to pregnancy. Contraception is defined as using any of the following methods:
 - condoms (male or female) with or without a spermicide
 - · diaphragm or cervical cap with spermicide
 - intrauterine device (IUD)
 - hormonal contraception
 - successful vasectomy in the male partner (considered successful if a woman reports that a male partner has [1] microscopic documentation of azoospermia, or [2] a vasectomy more than 2 years ago with no resultant pregnancy despite sexual activity post-vasectomy)
- or not be of reproductive potential, such as having reached menopause (no menses for one year) or having undergone hysterectomy, bilateral oophorectomy, or tubal ligation.
- and agree not to seek pregnancy through alternative methods such as artificial insemination or in vitro fertilization until last protocol visit.

Table 7-2 Study exclusion criteria

Participant has received any of the following substances:

- **HIV vaccine** in a prior HIV vaccine trial. For potential participants who have received control/placebo in an HIV vaccine trial, documentation of the identity of the study control/placebo must be provided to the HVTN 204 Protocol Safety Review Team to determine eligibility on a case-by-case basis.
- **Immunosuppressive medications** within 168 days before first vaccination, e.g., oral/parenteral corticosteroids, and/or cytotoxic medications. *Not excluded: (1)corticosteroid nasal spray for allergic rhinitis; (2) topical corticosteroids for mild, uncomplicated dermatitis; (3) a short course of rapidly tapered steroids (fewer than 10 days of treatment) more than 90 days before first vaccination*

Blood products within 120 days before first vaccination

Immunoglobulin within 60 days before first vaccination

Live attenuated vaccines within 30 days before first vaccination

Investigational research agents within 30 days before first vaccination

Medically indicated subunit or killed vaccines, e.g., influenza within 14 days, pneumococcal within 14 days, or allergy treatment with antigen injections within 30 days prior to initial study vaccine administration

Current anti-TB prophylaxis or therapy

Participant has a clinically significant medical condition, physical examination findings, clinically significant abnormal laboratory results, or past medical history with clinically significant implications for current health. A clinically significant condition or process includes but is not limited to:

- a process that would affect the immune response
- a process that would require medication that affects the immune response
- · any contraindication to repeated injections or blood draws
- a condition that requires active medical intervention or monitoring to avert grave danger to the participant's health or wellbeing during the study period
- a condition or process in which signs or symptoms could be confused with reactions to vaccine
- any condition specifically listed among the exclusion criteria below
- Any medical, psychiatric, or social condition, or occupational or other responsibility that, in the judgment of the investigator, would interfere with, or serve as a contraindication to, protocol adherence, assessment of safety or reactogenicity, or a participant's ability to give informed consent

Serious adverse reactions to vaccines including anaphylaxis and related symptoms such as hives, respiratory difficulty, angioedema, and/or abdominal pain. Not excluded: A participant who had a nonanaphylactic adverse reaction to pertussis vaccine as a

child.

Autoimmune disease

Immunodeficiency

Active syphilis infection. Not excluded: Syphilis fully treated over six months ago.

Asthma that is greater than mild in severity. Specifically excluded are participants with any of the following within the past year:

- · daily symptoms
- daily use of short acting beta2 agonists
- frequent exacerbations of symptoms that interfere with daily activity
- use of moderate to high dose inhaled corticosteroids (e.g. more than the equivalent of 250 mcg fluticasone; 400 mcg budesonide; 500 mcg beclomethasone; or 1000 mcg triamcinolone/flunisolide, as a daily dose) or theophylline
- emergent care, urgent care, hospitalization or intubation for asthma

Diabetes mellitus type I or type II, including cases controlled with diet alone. *Not excluded: Isolated gestational diabetes.* **Thyroid disease or thyroidectomy** requiring medication during the last 12 months.

Angioedema within the last 3 years if episodes are considered serious or have required medication within the last 2 years Hypertension that is not well controlled by medication, or blood pressure $\geq 150/100$ (either or both values) at enrollment Bleeding disorder diagnosed by a doctor, e.g., factor deficiency, coagulopathy, or platelet disorder requiring special precautions

Malignancy Not excluded: A participant with a surgical excision and subsequent observation period that in the investigator's estimation has a reasonable assurance of sustained cure and/or is unlikely to recur during the period of the study

Seizure disorder *Not excluded: A participant who had febrile seizures under the age of 3* **Asplenia:** any condition resulting in the absence of a functional spleen

Psychiatric condition that precludes compliance with the protocol. Specifically excluded are persons with any of the following:

- psychoses within the past 3 years
- ongoing risk for suicide
- history of suicide attempt or gesture within the past 3 years

Additional exclusion criteria for female participants: Pregnancy, or breast feeding, or plan to become pregnant during the period of study participation

8 Safety and immunogenicity evaluations

8.1 Considerations for trial start

Enrollment in this study will begin only after the combination of 4 mg of VRC-HIVDNA-009-00-VP DNA prime and 10¹⁰ PU of VRC-HIVADV014-00-VP adenoviral vector boost has been shown to be well tolerated in the HVTN 057 trial. The HVTN 204 Protocol Safety Review Team will review all of the data available 2 weeks after enrollment of at least 60 participants in HVTN 057. If necessary, an ad hoc unblinded review of the data will be performed by the HVTN Safety Monitoring Board (SMB).

8.2 Distinguishing intercurrent HIV infection from vaccine-induced positive serology

The study products may elicit an antibody response to HIV proteins. Therefore, vaccineinduced positive serology may occur in this study. Several precautionary measures will be taken to clarify this distinction:

- Participants will be counseled frequently during the trial on avoidance of HIV infection.
- Participants will be counseled on the risks of seeking HIV testing outside of the network during study participation, and discouraged from doing so.
- Participants will have clinical evaluations at visits specified in Appendix B. Signs or symptoms of an acute HIV infection syndrome, an intercurrent illness consistent with HIV-1 infection, or probable HIV exposure would prompt a diagnostic work-up per the standard HVTN algorithm to determine HIV infection.
 - Diagnostic HIV-1 ELISAs will be performed from blood draws at multiple time points throughout the trial (see Appendix A).
 - For US sites the HIV diagnostic Laboratory is Richmond. For Non-US sites, local labs may perform HIV diagnostic algorithms (following HVTN SOP) with pre-approval from the HVTN Laboratory Operations Division.

If intercurrent HIV-1 infection is suspected or positive test results are observed post-vaccination, the Laboratory Program or approved diagnostic laboratory will proceed with the HVTN algorithm to distinguish vaccine-induced antibody responses from actual HIV infection.

Continued follow-up will identify subsequent HIV infections or address concerns in participants whose HIV-1 ELISA is positive or indeterminate at the end of the study. All participants who have positive or indeterminate HIV-1 serology at the last study visit (as measured by the Abbott HIV 1, 2 kit or other standard anti-HIV antibody screening test used by blood banks) will be offered follow-up HIV-1 diagnostic testing (HIV-1 ELISA, Western blot, PCR) periodically and free of charge as medically/socially indicated (approximately every 6 months). This follow-up will be available until the ELISA/Western blot pattern no longer yields positive or indeterminate results or until HIV infection is confirmed.

Potential participants identified as being HIV infected during screening and participants who become HIV infected during the study will be referred for medical

treatment and management of the HIV infection. These individuals will also be referred to appropriate ongoing clinical trials or observational studies.

8.3 Immunogenicity evaluation

The ability of the vaccine to induce humoral responses and/or epitope-specific CD8+ and CD4+ T cell responses will be evaluated by the methods described below. For all assays, cryopreserved specimens from additional time points of immunological interest, as indicated in Appendix A, may be tested if positive responses are detected at the primary immunogenicity endpoints. All assays listed as primary immunogenicity endpoints must have undergone documented validation. Validation packages must be available for HVTN Laboratory Program and VRC review.

8.3.1 Humoral immunogenicity studies

8.3.1.1 Binding antibodies by ELISA (HVTN)

Binding antibodies to commercially available Env will be assessed at the HVTN-CL by ELISA using single serum dilutions (1/50 or 1/100) on samples from all study participants taken at the baseline and at the four week post last vaccination visit. Any of the time points that yield positive results, defined as an OD of ≥ 0.2 , in the initial ELISA may be subject to endpoint titration ELISA employing 6 (2-7-fold) serial dilutions of serum beginning at a 1/50 or 1/100.

8.3.1.2 Neutralizing antibody assay (HVTN)

HIV-1 specific neutralizing Ab assays will be performed on serum samples from all study participants taken at baseline and at the four week post last vaccination visit (see Appendix A). The assays will test neutralization of HIV-1 MN and the HIV-1 strains represented in the vaccine constructs (HXB2, Bal, 92rw020, and 97ZA012). The serum samples with the highest antibody response (as judged by either endpoint ELISA titer >100 or neutralization) may be further assayed against a panel of heterologous primary isolates and analyzed separately.

As an exploratory assay, the HVTN may examine neutralizing antibody responses against a panel of heterologous primary isolates using cross-sectional serum samples. If neutralizing antibodies are detected, a subset of samples with the best neutralizing activity will be screened at a single serum dilution for neutralization activity against a panel of heterologous strains.

8.3.1.3 Binding and neutralizing antibody assays (VRC)

Binding antibody to clades A, B, and C gp140 proteins will be performed by the VRC at the time points specified in Appendix A. Depending on the results of these assays, the VRC may perform Env-pseudovirus luciferase neutralization assays on panels of clades A, B, C and D viruses.

8.3.1.4 Neutralizing antibody against viral vector (Ad5)

The VRC laboratory will evaluate preexisting adenovirus neutralizing antibodies at screening and neutralizing antibodies produced against the adenoviral vector at four weeks post final vaccination.

8.3.2 Cellular immunogenicity studies

8.3.2.1 IFN-γ ELISpot (HVTN and VRC)

Ex vivo T cell responses will be assessed by IFN- γ ELISpot using cryopreserved peripheral blood mononuclear cells (PBMC) stimulated overnight with synthetic peptide pools that span the proteins encoded by the vaccine constructs. ELISpot assays will be performed at the baseline and at the four week post last vaccination visit by the VRC. ELISpot assays will be performed at the baseline and at the six week post last vaccination visit by the HVTN (see Appendix A). Responses will be reported as number of spot forming cells (SFC) per 10⁶ cells/well recognizing any specific peptide pool.

8.3.2.2 Intracellular cytokine staining (HVTN and VRC)

HVTN

Flow cytometry will be used to examine HIV-specific CD4+ and CD8+ T cell responses using intracellular cytokine staining (ICS) following stimulation with synthetic HIV peptides that span the proteins encoded by the vaccine construct. ICS assays will be performed at the baseline and at the six week post last vaccination visit (see Appendix A). Responses will be reported as percentages of CD4+ or CD8+ T cells expressing IFN- γ and/or IL-2 in response to any specific peptide pool.

VRC

A flow cytometric assay for the detection of ICS will be performed at the VRC Lab after stimulation with synthetic peptides that span the specific multiclade HIV-1 proteins encoded by the vaccine construct at baseline and at the four week post last vaccination visit (see Appendix A). Responses will be reported as percentages of T cells (CD4+, CD8+, both) expressing IFN- γ and/or IL-2 in response to any specific peptide pool.

8.4 HLA typing

Molecular HLA typing may be performed on enrolled participants using cryopreserved PBMC collected at baseline, initially in participants who demonstrate vaccine-induced T-cell responses at post-vaccination time points. Other participants (including placebo recipients) may be HLA-typed to support future studies of immunological interest at the discretion of the protocol chair and the Laboratory Program. These assays may include, but are not limited to, fine epitope mapping by flow cytometry or ELISpot, or flow cytometric tetramer analysis.

8.5 Ancillary studies

Cryopreserved samples may be used to perform additional ELISpot and ICS assays to support the standardization and validation of these assays, and in other immunological assays of interest to guide future research. These assays may include, but are not limited to, fine epitope mapping by flow cytometry or ELISpot, flow cytometric tetramer analysis, or genetic marker analysis.

9 Statistical considerations

9.1 Overview

The data analysis will characterize safety and immunogenicity data of the study products, a multiclade HIV DNA plasmid vaccine followed by a recombinant adenoviral vector vaccine boost.

9.2 Objectives

The primary objectives of this trial concern safety and immunogenicity of the study vaccines. The secondary objectives concern secondary immunogenicity endpoints and social impacts. See Section 6 for details.

9.3 Endpoints

9.3.1 Safety

Assessment of product safety will include clinical observation and monitoring of hematological and chemical parameters. Safety will be evaluated by monitoring participants for local and systemic adverse reactions after each injection and for 12 months after the first injection. Section 14 describes the safety monitoring plan and reports.

The following parameters will be assessed:

- Local reactogenicity signs and symptoms
- Systemic reactogenicity signs and symptoms
- · Laboratory measures of safety
- Adverse and serious adverse experiences

9.3.2 Immunogenicity

The primary immunogenicity endpoints are:

unfractionated IFN- γ ELISpot responses to HIV-1 peptide pools as performed by the VRC laboratory at Day 196. The data generated will contribute to the data package that the VRC/DAIDS will use to determine whether the products qualify for further evaluation in an efficacy trial.

unfractionated IFN- γ ELISpot responses to HIV-1 peptide pools as performed by the FHCRC laboratory at Day 210. The data generated will be used by the HVTN for independent evaluation of the products.

CD4+ and CD8+ T cell responses to HIV-1 peptide pools as measured by flow cytometry-based intracellular cytokine staining (ICS) assay as performed by the VRC laboratory at Day 196. The data generated will contribute to the data package to be used by the VRC/DAIDS to determine whether the products qualify for further evaluation in an efficacy trial.

• CD4+ and CD8+ T cell responses to HIV-1 peptide pools as measured by flow cytometry-based ICS assay as performed by the FHCRC laboratory at Day 210. The data generated will be used by the HVTN for independent evaluation of the products.

Secondary immunogenicity endpoints are:

- humoral immune response to HIV-1 as measured by neutralizing antibody and binding assays
- unfractionated IFN- γ ELISpot responses to HIV-1 as performed by the FHCRC or the VRC laboratories at Days 70, 210, and 364
- CD4+ and CD8+ T cell responses to HIV-1 as measured by flow cytometry-based ICS assay as performed by the FHCRC or the VRC laboratories at Days 70, 210, and 364
- Vaccine-induced HIV-specific T cell responses to individual peptide pools as measured by IFN-γ ELISpot and ICS as performed by the FHCRC or the VRC laboratories
- cross-clade cellular immune responses to HIV-1 Gag-Pol-Nef peptides from clades A and C as assessed by IFN-γ ELISpot and ICS assays as performed by the FHCRC or the VRC laboratories.

Other endpoints used in the immunogenicity assessment

• prior Ad5 antibody responses as measured by neutralizing antibody assay as performed by the VRC laboratory at baseline

9.3.3 Social impacts

Social impact variables include any negative experiences or problems the participant experienced due to his/her participation in this study. The following social impacts will be followed during the course of the study: social, travel, work, school, health care, life insurance, health insurance, housing, military and any additional impacts identified by a participant.

9.4 Accrual and sample size

Recruitment will target 480 healthy, HIV-uninfected adults. Within each of two regions (U.S./Caribbean and Southern Africa), 120 volunteers will be enrolled into the vaccine group and 120 volunteers will be enrolled into the placebo group. The total number of volunteers is 240 in the vaccine group and 240 in the placebo group. A large number of placebo recipients are included to permit robust characterization of safety and tolerability, and so that specimens from a subset of placebo recipients can be used to validate laboratory assays. Participants are enrolled without use of the data on preexisting Ad5 titers; that is these titers are not used as enrollment criteria. The study aims to enroll approximately equal numbers of men and women, such that at least 40% of the study population is male and at least 40% of the study population is female. If an interim assessment of the proportion of males and females enrolled reveals a large imbalance of one gender, future enrollments will seek to redress the imbalance.

Since enrollment is concurrent with receiving the first study vaccination, all participants will provide some safety data hence sample size calculations for safety in Section 9.4.1 are based on the target sample sizes. However this is not true of the immunogenicity data, therefore the sample size calculations in Section 9.4.2 account for 10% of enrolled participants having missing data for the primary endpoints, based on previous HVTN and AVEG studies.

9.4.1 Sample size calculations for safety

The goal of the safety evaluation for this study is to identify safety concerns associated with injection. Sample size calculations are expressed in terms of the ability to detect serious adverse experiences.

The sensitivity of the study to identify serious adverse experiences is best expressed by the maximum true rate of events that would be unlikely to be observed and the minimum true rate of events that would very likely be observed. Specifically, for the vaccine group where n=240, there is a 90% chance of observing at least one serious adverse experience if the true rate of such an event is at least 1.0%; there is a 90% chance that we would not observe at least one serious adverse experience if the true rate was no more than 0.05% (that is, 5/10,000 or less in the population). Probabilities of observing zero or two or more serious adverse experiences among a group of size 240 are presented in Table 9-1 for a range of possible true event rates. These calculations provide a more complete picture of the sensitivity of this study design to identify potential safety problems with the vaccine.

If none of the 240 participants receiving the vaccine experience life-threatening (grade 4) reactions to the given vaccine, the 95% exact two-sided upper confidence bound for the rate of such reactions in the population is 2%. If 10 of the 240 vaccinees experience such reactions, the upper bound for the rate is 9%. Suppose we assume based on data from previous AVEG studies that the rate of serious adverse events (SAEs) in controls is approximately 3.5%. Then for a two-sided exact test, type I error of 0.05, and power of 90%, the difference between a 3.5% SAE rate in the controls (n=240) and a 11.4% SAE rate in the vaccinees (n=240) is detectable.

Event rate	Pr(0/240 events)	Pr(1+/240 events)	Pr(2+/240 events)
0.05%	0.89	0.11	0.007
0.10%	0.79	0.21	0.025
0.50%	0.30	0.70	0.34
1%	0.09	0.91	0.69

Table 9-1 Probability of response for different safety scenarios for vaccinees (n=240)

9.4.2

Sample size calculations for immunogenicity

A primary objective is to characterize the immunogenicity of the two vaccine regimens. After accounting for a 10% dropout rate, the sample size of the vaccine group (n=216) allows a reasonable bound on the true response rates for the immunogenicity endpoints. For example, if the observed CD8+ T cell response rate is 70%, the exact 95% confidence interval is (63%, 76%). Confidence intervals of other response rates can be found in Table 9-2.

As sample sizes are large in this trial, there is sufficient power for a comparison of immune response rates between the control group (n=216) and the vaccine group (n=216). For example, a difference between a 3.5% control group (n=216) CD8+ T cell response rate and a 10.7% vaccine regimen response rate (n=216) is detectable with 80% power for a two-sided exact test with a Type I error rate of 0.05.

Table 9-2 Exact two-sided confidence intervals (CI) for the CD8+ T-cell response rate based on observing a particular rate of responses in vaccinees (n=216). CI's for larger loss-to-follow-up (LTFU) rates are also shown, n=204 with 15% LTFU, n=192 with 20% LTFU.

Observed response rate	95% CI (n=216)	95% CI (n=204)	95% CI (n=192)	
50%	(43%,57%)	(43%,57%)	(43%,57%)	
60%	(53%,67%)	(53%,67%)	(53%,67%)	
70%	(63%,76%)	(63%,76%)	(63%,76%)	
80%	(74%,85%)	(74%,85%)	(74%,85%)	
90%	(85%,94%)	(85%,94%)	(85%,94%)	

A secondary immunogenicity objective is to characterize the immune response rates of the vaccine regimen as a function of preexisting Ad5 antibody titer. Particular attention will be paid to the right tail of the function, where Ad5 titers exceed 1:500, as we wish to determine whether there exists a threshold Ad5 titer above which response rates are very low. The power calculations for this objective consider a series of 3 Fisher's Exact tests with Bonferroni adjustment for multiplicity to identify the presence of a threshold. Each tests for a difference in the number of positive responders above and below one of 3 fixed quantiles: 0.25, 0.50, 0.75. Response probabilities are simulated from a logistic model with pmax, pmin, and inflection point variables listed in Table 9-3. The slope of the model was set at -15 to give a sharp decline in response to mimic a threshold. The calculations in Table 9-3 assume n=100 vaccinees have pre-existing Ad5 titers > 1:500, after accounting for a 10% loss to follow-up rate. Note, there is over 80% power to detect a difference in response rates with at least one of the Fisher's Exact tests when pmax=40%, pmin=5% and the inflection point occurs at the 0.30 quantile. Power decreases when the inflection quantile equals 0.8 although arguably we are less concerned with such situations as they imply response rates are close to pmax for 80% of observed Ad5 titers > 1:500.

Table 9-3: Power to detect	difference in at least one	of the 3 Fisher's Exact tests.
----------------------------	----------------------------	--------------------------------

pmax	pmin Quar	tile of inflection	Power (n=100)
50%	10%	0.3	0.79
50%	10%	0.6	0.88
50%	10%	0.8	0.56
40%	10%	0.3	0.56
40%	10%	0.6	0.64
40%	10%	0.8	0.35
40%	5%	0.3	0.81
40%	5%	0.6	0.84
40%	5%	0.8	0.50

9.4.3

Sample size calculations across HVTN 204, RV172, and IAVI-V001

Taken together, the three studies, HVTN 204, RV172, and IAVI-V001, are well-powered to qualify the vaccine regimen for expanded studies of vaccine efficacy in the geographic regions of the trials (see Section 5.1). For each of the geographic regions, these studies will develop data that will enable: 1) bounding (by a 95% confidence limit) crude rates of serious adverse events related to vaccination to less than 3-6% if 0-2 such events are observed among the 120 vaccinees, and 2) detecting net rates of vaccine take to be greater than 30% if the true

rates of vaccine take are at least 47%. For example, HVTN 204 is able to detect differences in adverse event rates of 3.5% in the placebo arm versus 11% in the vaccine arm (or 3.5% versus 15% for immune response rates after accounting for 10% loss to follow-up). The immune response rate in the vaccine arm can be estimated with precision plus or minus 7%; for example, if the observed immune response rate is 50% in a given geographic region, then the 95% confidence interval about this rate is 40% to 60%. Power and precision are greater when the data from RV172 and IAVI-V001 are included in the analysis.

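### Section 9.4.1 gives 9% as the exact 95% upper bound for 10 events in 240 vaccinees; the correct value is 7.5% (8% in whole percent)

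*Protocol*

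**What the plan says.** Section 9.4.1 of the Protocol sets out what the trial can say about rare safety events, "for the vaccine group where n=240". It gives two confidence-bound examples for grade 4 reactions.

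- No events: "If none of the 240 participants receiving the vaccine experience life-threatening (grade 4) reactions to the given vaccine", then "the 95% exact two-sided upper confidence bound for the rate of such reactions in the population is 2" percent. This sentence fixes the method: exact, two-sided, 95%.
- Ten events: "If 10 of the 240 vaccinees experience such reactions, the upper bound for the rate is 9" percent. This sentence names no other method, so the same one applies.

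Section 9.4 explains the denominator: "all participants will provide some safety data hence sample size calculations for safety in Section 9.4.1 are based on the target sample sizes". The allowance for loss is attached to the immunogenicity calculations in section 9.4.2, which "account for 10% of enrolled participants having missing data for the primary endpoints".

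**The concern.** The sentence fixes everything needed to check it: 10 events, 240 vaccinees, and the exact two-sided 95% method carried over from the sentence before. The observed rate is 10/240 = 4.17%. An upper bound of 9% would lie 4.83 points above it, which is wide for a sample of this size.

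What is at stake is the accuracy of a stated precision figure. It is one of only two confidence-bound examples for grade 4 reactions in section 9.4.1, and safety is a primary objective. A reader who uses it to judge how well the trial bounds a reaction rate would think the trial less precise than it is.

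**Working it through.** **Inputs.** x = 10 events and n = 240 (section 9.4.1); two-sided 95%, exact (section 9.4.1, zero-event sentence). The upper limit therefore leaves 2.5% in the tail.

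**Step 1. Confirm the method on the neighbouring figure.** For zero events the exact upper limit is 1 − 0.025^(1/n). With n = 240 this is 1 − 0.025^(1/240) = 1.53%. The Protocol says 2%, which is right in whole percent.

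**Step 2. Apply the same method to 10/240.** The Clopper-Pearson upper limit is the value of p at which the chance of 10 or fewer events in 240 equals 0.025. Equivalently, it is the 0.975 quantile of a Beta(x + 1, n − x) = Beta(11, 230) distribution. The result is 7.53%, and the full interval is 2.0% to 7.5%. The stated 9% is not reproduced. The difference is 9 − 7.53 = 1.47 percentage points.

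**Step 3. Look for a reading that gives 9%.**

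| Calculation | Upper limit |
|---|---|
| 10/240, exact two-sided 95% (as stated) | 7.53% |
| 10/240, exact one-sided 95% | 6.97% |
| 10/240, Wald | 6.69% |
| 10/240, Wilson | 7.50% |
| 10/240, Wilson with continuity correction | 7.76% |
| 10/240, exact Poisson | 7.66% |
| 10/240, exact two-sided 97.5% | 8.05% |
| 10/240, exact two-sided 99% | 8.71% |
| 13/240, exact two-sided 95% | 9.08% |
| 10/216, exact two-sided 95% | 8.35% |
| 10/204, exact two-sided 95% | 8.83% |
| 10/200, exact two-sided 95% | 9.00% |
| 10/192, exact two-sided 95% | 9.37% |

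At n = 240 and 95%, nothing in the table exceeds 7.8%. To reach a value that rounds to 9%, one must change the confidence level to 99%, the count to about 13, or the denominator to roughly 190 to 210. The sentence states none of these.

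**Step 4. Check whether the error spreads.** The other figures in section 9.4.1 were recomputed at n = 240.

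- Table 9-1, Pr(0), Pr(1+) and Pr(2+):
  - 0.05%: 0.887, 0.113, 0.0066
  - 0.10%: 0.787, 0.214, 0.0245
  - 0.50%: 0.300, 0.700, 0.338
  - 1%: 0.090, 0.910, 0.693

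  All agree with the table.
- The text statement that "there is a 90% chance of observing at least one serious adverse experience if the true rate of such an event is at least 1.0" percent: 1 − 0.99^240 = 0.910. This holds.
- Power of the two-sided exact (Fisher) test for 3.5% against 11.4% with 240 per arm: 0.902, against the stated 90%. This holds.

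Only the 10/240 bound fails.

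**The case against.** The strongest reply is that the figure does no work. It is an illustration, it errs towards caution, and nothing is built on it. The sample size does not come from it. The rules in Table 14-2 act on a single participant with a related grade 4 event, not on a confidence bound. All of this stands and is why the point is minor, but it does not make 9% correct. Rounding is no defence either, since 7.53% becomes 8% in whole percent, just as 1.53% was given as 2%.

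A second reply is that 9% may have been worked out for a smaller group. With 10 events, 204 and 192 both round to 9%, and Table 9-2 uses those two sizes for larger loss to follow-up. A round 200 gives exactly 9.0%. The documents do not say where the figure came from, so any origin is a guess. The sentence itself names 240, and Table 9-2 concerns T-cell response rates.

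A reader might go further and infer that all the safety figures are overstated, because some vaccinees will be gone before the month-6 rAd5 injection and n = 216 should apply. The documents do not support this.

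- Section 9.4 gives its reason for using the target size: everyone enrolled has had the first injection and contributes safety data. Section 9.5 matches it by analysing all enrolled participants as randomized, however many injections they received.
- Section 9.4 defines the 10% as missing data for the primary endpoints, in the immunogenicity calculation. Those assays fall on Days 196 and 210, after the Day 168 boost. Section 9.4.2 calls it a dropout rate ("After accounting for a 10% dropout rate, the sample size of the vaccine group (n=216"), but does not say that the loss occurs before the boost. Someone boosted may lack an assay result, and section 14.5.2 encourages participants whose injections are stopped to stay in follow-up.
- The 90% detection statement is made for n = 240, where it is correct.

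Fewer than 240 may in fact receive rAd5. If 216 is assumed purely for illustration, the zero-event bound moves from 1.5% to 1.7% (still 2% as stated), and the chance of seeing at least one event at a 1% rate moves from 91.0% to 88.6%. Neither is an error in the plan. A fall in power to 86.3% for 3.5% against 11.4% would also rest on that assumption, and the comparison stated in section 9.4.1 uses 240 per arm.

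**Conclusion.** The 9% in section 9.4.1 is wrong. By the method, count and denominator given there, the upper bound is 7.5% (8% in whole percent). The error is about 1.5 percentage points, on the conservative side, and confined to this one sentence. Severity is minor.

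The conclusion rests on one assumption: that the exact two-sided 95% method named for the zero-event case also governs the sentence that follows. It is not sensitive to that, since every 95% alternative tried at n = 240 stays below 8%. The finding does not extend to the choice of n = 240 for safety.

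**What to change.** In section 9.4.1, change the upper bound for 10 of 240 vaccinees from 9% to 7.5%, or to 8% if whole percents are kept to match the 2% beside it. No other figure in the section needs to change. The cost is one number, with no effect on design, sample size, analysis or safety monitoring.
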